
Study Rationale	
According to the findings of mechanism-based studies, rhTPO competes with endogenous TPO for binding to TPO-R while eltrombopag has an additive effect with endogenous TPO¹⁰, indicating that the treatment mechanism and side-effect profiles could be somewhat different between these drugs^{9, 10}. Therefore, when there's a lack of response or when adverse events become a problem with one TPO-RA, switching to another TPO-RA provides useful information for the management of adult ITP patients^{8, 9}.
 
Khellaf et al. retrospectively reviewed data of 46 ITP patients who sequentially switched from eltrombopag to romiplostim (a TPO-RA similar to rhTPO in mechanism) or vise versa due to varying reasons including lack of efficacy (n=23), platelet-count fluctuations (n=11), side effects (n=4), and patient's preference (n=8). Switching was shown effective in 50-80% of the patients, with eradication of platelet fluctuations in 54% and side effects resolved in 100%¹. Another retrospective analysis of 26 ITP patients showed that for patients who switched the TPO-RA as a result of inefficiency (n=10), switching from romiplostim to eltrombopag led to 100% response rates, whereas switching from eltrombopag to romiplostim led to 66% response rates. The response rate was 100% in patients who switched due to side effects (n=5) or patient preference (n=8)¹⁰. In a study of 51 primary ITP adult patients switching from romiplostim to eltrombopag, response rate was 80% (41/51) with efficacy maintained for a median of 5.5 (range, 2-9) months in all patients who switched because of patient preference (n = 16), platelet-count fluctuation (n = 6) and side-effects (n = 4)⁹. Cantoni et al. analyzed clinical characteristics associated with response to the switch of TPO-RAs and found that lines of previous therapy, as well as disease duration would lower the probability to respond. According to the study, response was achieved/regained in 57.8% of patients who switched for efficacy issues and 80% who switched for non-efficacy issues; once response to the 2nd TPO-RA is achieved, it is possible to maintain long-term effect in these patients³.
 
Based on the clinical evidence, it is shown that switching from one TPO-RA to another, as well as sequential therapy, provides favorable outcomes of response and tolerability (evidence levels IIb, III)⁸. However, current studies almost exclusively focus on the effect of switching between romiplostim and eltrombopag; whether there is also absence of cross-resistance between rhTPO and eltrombopag remains to be investigated. In addition, clinical evidence on TPO-RA switching is proposed on the basis of retrospective studies. Therefore, we propose here an observational study with retrospective and prospective design to evaluate the response and safety profiles of switching between eltrombopag and rh-TPO in Chinese adult ITP patients; the preference of patients and doctors will also be assessed in this study.

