Endpoints	
Primary endpoint:
 
 ➤ Rate of response at 6 weeks after switching from rhTPO to eltrombopag or vice versa 
Response is defined according to the Chinese guidelines for treatment of adult primary immune thrombocytopenia as ⁷:
 
Complete response (CR): platelet count $\geq 100 \times 10^9/L$ and absence of bleeding.
 
Response (R): platelet count range $30-100 \times 10^9/L$, at least doubling of the baseline count, and absence of bleeding.
 
No response (NR): platelet count $< 30 \times 10^9/L$, or less than doubling of the baseline count, or bleeding.
 
The rate of response at 6 weeks includes the total proportion of patients who achieved CR and R at 6 weeks in the groups switch from rhTPO to eltrombopag and eltrombopag to rhTPO, respectively.
 
Secondary endpoints:
 
 ➤ Rate of response at 6 weeks after switching, according to the reasons of switching 
The reasons of switching include ³:
 
Lack of efficacy:
 
 -1st TPO-RA failure: no response to either one TPO-RA administered before switch -Loss of response: relapsed after transient response to 1st TPO-RA (relapse is defined as platelet count $< 30 \times 10^9/L$, or less than doubling of the baseline count, or bleeding, after the achievement of CR or R. The blood platelet count should be confirmed on at least two separate occasions, which is at least 1 day apart when used to define relapse ⁷) 
Platelet count fluctuations: unstable platelet counts necessitating rescue therapy or transient TPO-RA dose modifications/withdrawal with associated risk of either rebound thrombocytopenia/bleeding or thrombocytosis
 
Patient's preference
 
Development of adverse events necessitating 1st TPO-RA discontinuation
 
 ➤ Proportion of patients who achieved, regained, and maintained response at 6 weeks after switching 
Response achieved refers to patients who failed the 1st TPO-RA achieve CR or R at 6 weeks after switching.
 
Response regained refers to patients who lost response to the 1st TPO-RA achieve

CR or R at 6 weeks after switching.

Response maintained refers to patients who achieved CR or R with the 1st TPO-RA and still respond to the 2nd TPO-RA at 6 weeks after switching.

- Rate of response at 3 months after switching from rhTPO to eltrombopag or vice versa

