	
3 months after switching.
 
The observation period is 3-month for each patient enrolled. Response to 2nd TPO-RA will be assessed throughout the observation period with response at 6 weeks being the primary evaluation. Adverse events, including bleeding events, will be assessed and recorded together with concomitant ITP treatment. Preference of patients and doctors on the two TPO-RAs will also be assessed.

Investigational Drug Administration	
Patients will initiate eltrombopag treatment with a dose of 50 mg once daily. Dose adjustment of study medication will be allowed to maintain platelet counts between 50*10⁹/L and 250*10⁹/L.
 
Patients will initiate rh-TPO with a dose of 300 U/kg/d for \leq14d. Patients who attained stable PLT counts (\geq50*10⁹/L) in two consecutive tests will enter maintenance therapy, starting with every other day administration of rhTPO, then adjust dose interval to maintain platelet counts at 30-100*10⁹/L.

Dose Adjustment Guidelines	
The following information serves as a reference; actual dose adjustment will be conducted according to clinical practice in considering the medical condition of a patient:
 
Eltrombopag: refer to Table 2.
 
RhTPO:
 
At initial treatment, rhTPO will be suspended when platelet counts \geq100*10⁹/L. During maintenance therapy, patients with platelet counts $>$150*10⁹/L will suspend treatment until platelet counts drop to \leq150*10⁹/L. Dosing interval will be prolonged when platelet count is \geq100*10⁹/L to \leq150*10⁹/L. Dose modification is not required when platelet count is \geq30*10⁹/L to $<$100*10⁹/L¹³.

Patient Population	Chinese adult patients with primary immune thrombocytopenia who failed first-line corticosteroid therapy and received rhTPO and then switch to eltrombopag or vice versa.
Key Inclusion Criteria	
 • Age 18 years or older • Chinese ethnicity • Primary ITP diagnosed according to the current definitions ^{7, 8, 14, 15} • Failed initial glucocorticosteroid treatment, • Applying rhTPO or Eltrombopag as subsequent treatment • Switch from rh-TPO to eltrombopag or vice versa • Treatment on rhTPO for 14 days minimum or Eltrombopag for 4 weeks minimum, if the reason of switching is lack of efficacy or platelet count fluctuations • Available follow-up at least 6 weeks after switching

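### Loss of response is defined without asking whether the first TPO-RA was still being given, so relapses after rhTPO has stopped can be counted as lack of efficacy and can inflate the by-reason response results

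*Combined protocol and SAP*

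**What the plan says.** In the Combined protocol and SAP, Endpoints (secondary endpoints, reasons of switching), lack of efficacy has two parts: failure of the first TPO-RA, and "Loss of response: relapsed after transient response to 1st TPO-RA". Relapse is a count below 30 × 10⁹/L, "or less than doubling of the baseline count, or bleeding, after the achievement of CR or R". One condition is added: "The blood platelet count should be confirmed on at least two separate occasions, which is at least 1 day apart".

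A separate reason, platelet count fluctuations, covers unstable counts that call for rescue therapy or "transient TPO-RA dose modifications/withdrawal with associated risk of either rebound thrombocytopenia/bleeding or thrombocytosis". No text says which reason applies when a patient fits both.

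Key Inclusion Criteria sets a minimum exposure: "Treatment on rhTPO for 14 days minimum or Eltrombopag for 4 weeks minimum, if the reason of switching is lack of efficacy". The same minimum applies when the reason is platelet count fluctuations.

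Investigational Drug Administration describes rhTPO as a time-limited start ("Patients will initiate rh-TPO with a dose of 300 U/kg/d", for at most 14 days), with maintenance for patients whose counts are stable. Dose Adjustment Guidelines describes suspension at 100 × 10⁹/L or above during initial treatment. Eltrombopag is described as once daily, with no stated course length.

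Study Rationale names the open question: "whether there is also absence of cross-resistance between rhTPO and eltrombopag remains to be investigated".

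**The concern.** A fall in platelets while the first drug is being taken is evidence that the drug has stopped working. A fall after the drug has ended may show only that it was withdrawn. The definition treats the two alike. A patient of the second kind has shown sensitivity to the first TPO-RA, so a later response to the other drug says little about cross-resistance, yet it would count as a response regained after lack of efficacy.

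The results that use this label are:

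- the lack-of-efficacy response rate at 6 weeks and 3 months;
- the regained proportion at both times;
- time to response and duration of response, which are restricted to efficacy switchers;
- two exploratory predictors: efficacy versus non-efficacy switch, and first-drug failure versus loss of response.

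The problem is more likely after rhTPO, whose initial course is time-limited and whose 14-day minimum is met by completing that course. Because an off-drug fall can also be coded as a fluctuation, two sites could classify the same history differently.

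**Working it through.** **1. Can such a patient enter under this label?** Take a patient who reaches CR or R on rhTPO, completes 14 days, does not go on to maintenance, and later has counts below 30 × 10⁹/L on two occasions at least 1 day apart.

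- Minimum exposure (14 days of rhTPO): met.
- Transient response, then relapse after CR or R: met.
- Confirmation: met.
- Any condition on current dosing or time since last dose: none exists.

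The patient is a loss of response as written, and arguably a fluctuation as well.

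**2. Inputs.**

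- Study Rationale, cited Italian survey: response 57.8% in efficacy switchers and 80% in non-efficacy switchers.
- Study Rationale, cited review of 46 patients: 23/46 = 50% switched for lack of efficacy.
- Sample Size Justification: 80 patients, inflated for 20% drop-out. 80/(1 − 0.20) = 100, which reproduces the planned total. The plan states no figure for the loss-of-response group.
- Not in the documents, so assumed: *f*, the share of the lack-of-efficacy group whose relapse was off drug, and *p_off*, their response rate on the second drug. The 57.8% is taken as the rate without off-drug relapsers.

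**3. Bias within the affected sequence.** Observed rate = (1 − f) × 57.8% + f × p_off, so bias = f × (p_off − 57.8%).

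| p_off | f = 25% | f = 50% |
|---|---|---|
| 57.8% | 0 | 0 |
| 70% | 0.25 × 12.2 = +3.05 | 0.50 × 12.2 = +6.1 |
| 80% | 0.25 × 22.2 = +5.55 | 0.50 × 22.2 = +11.1 |
| 100% | 0.25 × 42.2 = +10.55 | 0.50 × 42.2 = +21.1 |

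At p_off = 80% the observed rate would be about 63.3% or 68.9% instead of 57.8%. A p_off below 57.8% would reverse the sign.

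**4. Pooled over sequences.** The by-reason endpoint is not stated to be split by sequence. If efficacy switchers are equally divided and only one sequence is affected, the p_off = 80% figures halve: 5.55/2 ≈ 2.8 and 11.1/2 ≈ 5.6 points.

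**5. Effect on the efficacy versus non-efficacy contrast.** Without off-drug relapsers it is 80 − 57.8 = 22.2 points. With f = 50% in one sequence, the pooled share is 25% and the contrast falls to 80 − 63.35 ≈ 16.7 points. As an illustration, assume 80 evaluable patients, half of them efficacy switchers (40 versus 40), and a two-sided 5% test with power = Φ{[Δ − 1.96√(2p̄(1 − p̄)/n)] / √[(p₁q₁ + p₂q₂)/n]}. Power falls from 57.5% to 37.7%.

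**6. Against sampling error.** The 95% half-width at 57.8% is 1.96 × √(0.578 × 0.422/n): 21.6 points for n = 20 (one sequence) and 15.3 points for n = 40 (pooled).

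**The case against.** A reader might infer that every platelet fall after rhTPO ends will be counted as lack of efficacy, and that the rhTPO-to-eltrombopag result is therefore inflated. The documents do not support that, for these reasons.

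- Platelet count fluctuations can also take withdrawal-related falls, and the reason for switch comes from medical records, so coding as lack of efficacy is possible rather than automatic.
- The pool is narrower than it first appears. If first-drug courses follow the dosing text, responders with two consecutive stable counts are meant to enter maintenance and so remain on drug. Those stopped before day 14 who do not resume miss the 14-day minimum. The dosing text also describes study treatment, whereas a first rhTPO course precedes enrolment.
- Neither f nor p_off is documented. Whether the cited 57.8% already includes off-drug relapsers cannot be checked from the plan.
- The plan says its purpose is not to compare the two sequences, and the definition would equally admit an off-drug fall after eltrombopag.
- Most of the shifts above are smaller than the sampling error.
- Whether relapse after a short course is inefficacy is partly a matter of definition, and the plan attributes its reason categories and its relapse definition to cited sources.

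All of this stands, and it limits the claim to a possible bias of unknown size. It does not close the gap. The overlap with fluctuations, without a precedence rule, is itself a reason to act. A confidence interval does not show misclassification, and results cannot be re-sorted later if the dates were never abstracted.

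**Conclusion.** The definitional gap is real. As written, loss of response admits relapse after a completed or suspended first TPO-RA course, and this can inflate the lack-of-efficacy response rate and the regained proportion at 6 weeks and 3 months. It can also affect time to and duration of response in efficacy switchers, in a direction the documents do not settle, and blur the two exploratory predictors.

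For f between 25% and 50%, the shift within the affected sequence is about 5.5 to 11.1 points if off-drug relapsers respond like the cited non-efficacy switchers, and zero if they respond like the efficacy switchers. Taking p_off from 57.8% to 100%, the range for f up to 50% is 0 to about 21 points. Pooling equal numbers with one sequence affected halves these figures. All of them rest on assumed values of f and p_off.

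A reader might also infer that the main result is at risk. It is not: the primary endpoint does not use switch reasons. The achieved proportion, which concerns first-drug failures and is the most direct evidence on cross-resistance, is defined separately and is unaffected.

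**What to change.** The change concerns definition and analysis only; how either drug is given or stopped is unchanged.

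1. In Trial Design, specify that the record review of the first TPO-RA includes its last-dose date and the relapse date.
2. In Endpoints, split loss of response into (a) relapse on the first TPO-RA, or within a stated window after its last dose, and (b) relapse off the first TPO-RA, meaning later than that window. Fix the window before the data are analysed.
3. Add a precedence rule against platelet count fluctuations. One workable form: a confirmed relapse after CR or R is coded (a) or (b), and fluctuations is used only where there is no such relapse.
4. In Statistical Analysis, report the lack-of-efficacy rate, the regained proportion, time to and duration of response, and the two predictor comparisons with and without category (b). Showing both avoids having to settle whether off-drug relapse is inefficacy.
5. Base statements about cross-resistance on first-drug failures and on-drug relapses.

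The cost is two dates from records already under review, one extra reason code, and a somewhat smaller subgroup in the analyses without category (b).

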- Rate of response at 3 months after switching, according to the reasons of switching
- Proportion of patients who achieved, regained, and maintained response at 3 months after switching
- Time to response from 1st TPO-RA switching for patients who switch due to lack of efficacy
- Duration of response from 1st TPO-RA switching for patients who switch due to lack of efficacy

Duration of response is defined as the time from when CR or R is achieved/regained to the time of relapse.

- Proportion of patients with any bleeding (WHO bleeding scale grade 1–4¹¹) and clinically significant bleeding (WHO bleeding scale grade 2–4¹¹)
- Total score of bleeding calculated according to the Bleeding Rating System⁷
- Patient and physician's treatment preference

At 6 weeks after switching, patients will be asked whether they prefer to continue treatment with rhTPO or eltrombopag, or whether they had no preference¹². In addition, patients who prefer one TPO-RA over the other will be queried on the reasons of preference (Patient preference questionnaire attached as Appendix 1).

At 6 weeks after switching, physicians will also be asked whether they prefer to further treat the patient with rhTPO or eltrombopag, or whether they had no preference, taking into account the patient's preference, response, and tolerability¹².

At 3 months after switching, the measurement will be applied again.

- Safety of treatment

The safety of treatment will be determined from adverse events summarized by incidence and severity, and from clinical laboratory evaluations, physical examinations and ophthalmological examinations carried out during scheduled study visits.

Exploratory endpoints:

- Association between clinical characteristics and response after switching

The following clinical characteristics will be compared between responders and non-responders at 6 weeks and 3-month after switching, respectively: gender (male vs female), age at 1st TPO-RA, time from diagnosis to 1st TPO-RA, lines of previous therapy before 1st TPO-RA, maximum 1st TPO-RA dose received vs. not received, splenectomy status (yes vs no), switch sequence (rhTPO to eltrombopag or vice versa), switching behavior, switch due to efficacy vs non-efficacy issues, and 1st TPO-RA failure vs loss of response.

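### Relapse needs two platelet counts but response has no confirmation rule, so time to response and duration of response hang on single counts and on how often each switch sequence is tested

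*Combined protocol and SAP*

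**What the plan says.** All references are to the combined protocol and SAP.

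- **Endpoints, response.** CR is a count of at least 100 x 10^9/L without bleeding. R is a count of 30-100 with "at least doubling of the baseline count, and absence of bleeding". Neither has a repeat count or a minimum length.
- **Endpoints, relapse.** The confirmation rule is tied to relapse: "The blood platelet count should be confirmed on at least two separate occasions, which is at least 1 day apart when used to define relapse". It covers the platelet count; bleeding needs no repeat.
- **Endpoints, time-to-event.** Time to response is named for patients who switch for lack of efficacy, with no event rule beyond CR or R. "Duration of response is defined as the time from when CR or R is achieved/regained to the time of relapse".
- **Endpoints, 1st-drug labels.** Lack of efficacy splits into "1st TPO-RA failure: no response to either one TPO-RA administered before switch" and "Loss of response: relapsed after transient response to 1st TPO-RA". The split carries forward: "Response achieved refers to patients who failed the 1st TPO-RA achieve CR or R at 6 weeks after switching", while "Response regained refers to patients who lost response to the 1st TPO-RA achieve" CR or R at that time. Failure versus loss of response is also an exploratory covariate.
- **Table 1, footnotes a and b.** After a switch to rhTPO, blood counts are every other day in initial treatment, then weekly. After a switch to eltrombopag they are weekly until stable, then every 4 weeks. Weekly visits have a window of 3 days either way.
- **Statistical Analysis.** Time-to-event data get Kaplan-Meier curves and a log-rank test between groups. The groups are not named.

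**The concern.** The start and end of a response are held to different standards. One high count opens the response, while one low count does not close it. The study expects unstable counts, since it lists this switch reason: "Platelet count fluctuations: unstable platelet counts necessitating rescue therapy".

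Two things are at stake. First, a chance high count in a patient with no real response sets an event date for time to response and starts the duration clock. The chance of this rises with the number of counts, and that number differs by switch sequence because the monitoring schedule differs. A Kaplan-Meier or log-rank comparison of the two sequences would then partly compare visit schedules.

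Second, a loss of response needs only a transient response of no stated length. One qualifying count in the 1st-drug records could therefore move a patient from failure to loss of response, and so from the achieved group to the regained group.

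**Working it through.** The plan states no figure on this point, so there is nothing of its own to reproduce. The first two steps use the documents; the rest is illustration under stated assumptions.

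**1. Text.** The definitions of CR, R, no response, relapse, time to response and duration were set side by side. Only relapse has a repeat-count rule, and no other section adds one for response.

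**2. Counts by week 6.** Initial rhTPO lasts up to 14 days: 14/2 = 7 counts, then 4 weekly counts (days 21, 28, 35, 42), total 11. Eltrombopag: 6 weekly counts.

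**3. Model (assumed).** A true non-responder has log-normal counts with median equal to baseline b, log-SD s, and correlation r between counts a week apart (r to the power days/7 at other gaps). Bleeding is ignored. The count needed is T = max(30, 2b), and the chance per count is q = 1 - Phi(ln(T/b)/s).

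- b = 15 to 20: T/b = 2, ln 2 = 0.693. q = 4.2% at s = 0.4 and 8.3% at s = 0.5.
- b = 10: T/b = 3, ln 3 = 1.099. q = 0.3% and 1.4%.
- b = 5: T/b = 6, ln 6 = 1.792. q is at most about 0.02%.

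**4. Closed form with independent counts.** P(at least one) = 1 - (1 - q)^k.

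- s = 0.4: 1 - 0.9584^6 = 22.5%; 1 - 0.9584^11 = 37.3%.
- s = 0.5: 1 - 0.9172^6 = 40.5%; 1 - 0.9172^11 = 61.4%.

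**5. Simulation** (200,000 patients per setting). Confirmed means two qualifying counts at least 7 days apart with every count between them also qualifying. Each cell shows r = 0 / r = 0.5.

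| Baseline | s | Weekly, single | Frequent, single | Weekly, confirmed | Frequent, confirmed |
|---|---|---|---|---|---|
| 15-20 | 0.3 | 6% / 5% | 11% / 7-8% | under 1% | under 1% |
| 15-20 | 0.4 | 23% / 19% | 37% / 24% | 1% / 4% | 1% / 4% |
| 15-20 | 0.5 | 41% / 33% | 61% / 41% | 3% / 9% | 3% / 9% |
| 10 | 0.4 | 2% / 2% | 3% / 2% | under 1% | under 1% |
| 10 | 0.5 | 8% / 7% | 14% / 10% | under 1% | under 1% |
| 5 | 0.4-0.5 | about 0% | about 0% | about 0% | about 0% |

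At baseline 15-20, the median day of the first false response is 10-12 on the frequent schedule and 21 on the weekly one. Confirmation almost closes the gap between schedules.

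**6. Visit window.** If weekly visits fall evenly on days -3 to +3, two adjacent visits are under 7 days apart with probability 21/49 = 43%. A strict 7-day gap would reject many ordinary weekly pairs, so the rule should use the nominal week.

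**The case against.** **Silence is not a rule.** The plan does not say that one count is enough, and it takes its definitions from a guideline not available here. This stands as a limit on wording: the point is that the plan states no rule, and that one count meets CR or R as written.

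**Few endpoints are touched.** A reader might infer that the primary result is inflated. The documents do not support that: the overall rates are read at 6 weeks and 3 months, so an earlier spike does not change them, and no endpoint counts patients who responded at any time. Achieved and regained are both within lack of efficacy, so a shift between them leaves their combined number unchanged.

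**Misclassified 1st-drug labels are not shown.** Under Trial Design the switch reason is collected from medical records, and nothing says it is derived from single counts. The documents give no count schedule for the 1st drug, a short response fits the loss-of-response wording, and fluctuation has its own category. The effect on labels is therefore possible, not established.

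**The size depends on baseline.** This stands. Below a baseline of 15 the floor of 30 binds and the chance falls quickly. Bleeding would lower it further.

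**Duration has no clear direction.** False starts add very short durations, while confirmed relapse lengthens them. This also stands.

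**The fix has its own asymmetry.** Relapse would be confirmed a day apart and response about a week apart. In the first 14 days an rhTPO patient would need four or five qualifying counts in a row, against two on eltrombopag. The plan also suspends initial rhTPO at 100 or above, so a response may fade after a planned suspension. For non-responders the two schedules come out nearly equal in the simulation; true responders with variable counts could still be held to a stricter test on rhTPO. This is a reason to show both versions.

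**Conclusion.** The point holds for time to response and for the start, and hence the length, of duration of response. It holds as a possibility for the failure versus loss-of-response label, the achieved versus regained split and that exploratory covariate. It does not hold for the fixed-time overall rates.

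The part that follows from the documents alone is the schedule effect: about 11 counts against 6 by week 6 means that, under a single-count rule, equal drugs would not look equal on time to response. This matters only if sequences are compared. The plan disclaims an efficacy comparison under Sample Size Justification but leaves the log-rank groups open.

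The size is conditional. With log-SD 0.4-0.5 and weekly correlation 0-0.5, about 19-41% (weekly) or 24-61% (frequent) of true non-responders have at least one qualifying count by week 6 at baseline 15-20, 2-8% or 2-14% at baseline 10, and almost none at baseline 5. Confirmation about a week apart gives 9% or less throughout. The spread, correlation and baselines are assumptions. This should be settled before analysis, but it does not threaten the primary endpoint.

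**What to change.** - For time to response and duration of response, require CR or R to be confirmed at the next scheduled weekly count (nominally one week, visit window allowed), with no non-qualifying count between. Date the response to the first count.
- Censor a first qualifying count that falls at the last visit.
- Report the single-count version as a sensitivity analysis.
- Apply the same rule to the failure versus loss-of-response label where the 1st-drug records hold repeat counts. Otherwise keep the recorded reason and report how many labels could not be confirmed.
- Leave the week-6 primary rate as defined.

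The cost is SAP wording and derivation code. Counts already scheduled should normally suffice: eltrombopag testing thins to every 4 weeks only after at least 4 weeks at 50 x 10^9/L or above. The downside is somewhat fewer responders in the time-to-event endpoints and some 1st-drug labels that cannot be confirmed.
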